12.2. ANALYSIS OF OUTCOME MEASURE

The statistical analyses will be described in detail in a statistical analysis plan (SAP). All of the tests will be two-sided with an alpha level of 0.05.

12.2.1. PRIMARY OUTCOME:

The overall prevalence will be estimated as the number of patients with HPV detected in tonsils divided by the total number of patients with available samples. An exact 95% confidence interval will be computed. The prevalence per age and gender group will be calculated similarly.

The relationship between prevalence and age will be explored using logistic regression with the age as a continuous covariate and gender and centre as categorical covariate. The number of degrees (one, two, three) of the model and possible variable transformation (e.g. log-transformation of age) could be determine based on graphical analysis of prevalence versus age relationship and on model fit criteria (e.g. AIC).

12.2.2. SECONDARY OUTCOME:

The overall prevalence will be estimated as the number of patients with HPV detected in oral fluid, oropharyngeal scrapes and urine samples divided by the total number of patients with available samples. An exact 95% confidence interval will be computed.

The prevalence per age and gender group will be calculated similarly. Prevalence rate will be compared among centres using a Cochran-Mantel-Haenszel test with stratification by age group.

Relationship between the prevalence of HPV in tonsils and the prevalence of HPV in oropharyngeal scrapes, oral fluid, and urine samples will be analysed by computing kappa coefficient. Specificity, sensitivity, positive predictive value and negative predictive value of HPV detection in the different sample types will be derived using the oral sample results as the reference.

Relationship between presence of anti-HPV L1 antibody in oral fluid samples and occurrence of HPV in tonsils and/or in oropharyngeal scrape samples will be analysed by computing kappa coefficiency. Specificity, sensitivity, positive predictive value and negative predictive value of anti-HPV L1 antibody assay will be derived using the oral sample results as the reference.

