The rate of HPV persistence will be calculated as the proportion of baseline HPV-positive patients who again test HPV-positive in oral fluid, fingertip/nail brushings and urine samples collected after approximately 3 - 6 months. The rate of oral HPV infection clearance will be calculated as the proportion of baseline HPV-positive patients who test HPV-negative in oral fluid, fingertip/nail brushings and urine samples collected after approximately 3 - 6 months.

HPV incidence will be calculated as the proportion of baseline HPV-negative patients who test HPV positive in oral fluid, fingertip/nail brushings and urine samples collected after approximately 3 - 6 months. Exact 95% confidence intervals will be computed.

Multi variable regression models will be used to calculate the odds ratios of different risk factors for having HPV DNA in the tonsil and in the oropharynx, Variables to be included in the model (e.g. serological markers and clinical risk factors such as HPV vaccination status, tobacco and alcohol use) will be selected on the basis of descriptive statistics/possible causal relationship and/or a stepwise approach. Analysis of results may be performed to identify a possible marker or combination of markers for screening for persistent HPV infections in the oropharynx.

Among females in the target age class for vaccination (12 to 24 years), exploratory analyses will compare the HPV prevalence rate in HPV vaccinated and non HPV vaccinated patients using a Fisher's exact test. Association between HPV vaccine and oral HPV infection will be assessed using a case-control approach. Cases will be patients with HPV positive oral sample and controls will be patients with HPV negative oral sample. The exposure to vaccine will be compared between the case and the control groups using logistic regression, OR and its 95% confidence interval will be derived.

Prevalence of HPV in tonsils will be described and compared between the current cohort and the comparison historical cohort using a Cochran-Mantel-Haenszel test with stratification by age group and gender.

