12.3. SAMPLE SIZE CONSIDERATIONS

An analysis of current literature suggests that in a population recruited between 1990 and 2000, the prevalence of oral HPV was about 6.5%, varying from 0% - 10%. However, in an analysis of oropharyngeal scrapes and oral washings, the prevalence of HPV detection was much higher at 31%.

Pilot data of patients having tonsillectomy at University Hospital Coventry over two 3-month time periods are shown below in table 3. The number of tonsillectomy operations performed at the Heart of England NHS Foundation Trust - is approximately 50% of that for University Hospital Coventry quoted below.

Table 5: The number of tonsillectomy operations performed at University Hospital Coventry.

Age Group*	Number of Monthly recruitment (%)		
0-4	7 (12%)		
5-9	12 (20%)		
10-14	7 (12%)		
15-19	10 (17%)		
20-24	6 (10%)		
25-29	5 (8%		
30-34	4 (7%)		
35-39	5 (8%)		
40-44	1 (2%)		
45-49	1 (2%)		
50-69	1 (2%)		
Total	59		

^{*}There was an equal distribution of males and females in the group.

We plan to enrol 925 patients. The precision of the overall prevalence estimate that would be achieved with such a number is summarised in Figure 1 for prevalence ranging from 1 to 31 %. For example, if the observed prevalence is 10 %, the 95 % confidence interval for the overall population will be 8.4 to 11.8 % corresponding to a relative precision of 17 %.

[figure not shown]

Figure 1: Precision (95% confidence interval) of the prevalence estimate versus the prevalence observed in a random sample of 1250 patients.

We will also undertake a stratified sampling strategy to allow comparisons between those aged 14 and under (non-exposed, approximately one third of the cohort), and patients over 14 years of age (exposed) to allow the determination of the age of acquisition of infection and the optimal age of start of vaccination. The stratified sampling strategy will recruit patient subgroups as follows:

Table 6: The stratified sampling strategy for patient recruitment.

Age group	Sample size (%)		
0-4	150 (16.5%)		
5-9	150 (16.5%)		
10-14	150 (16.5%)		
15-19	150 (16.5%)		
20-24	150 (16.5%)		
25-34	100 (11%)		
35-44	60 (5.5%)		
45-65	15 (1.0%)		
Total	925		

[figure not shown]

Figure 2: Precision (95% confidence interval) of the prevalence estimate versus the prevalence observed in a random sample of 100, 150, and 250 patients.

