12.4. POWER CALCULATIONS

For the historical comparison analysis, assuming a two-sided test, 0.05 alpha level, baseline prevalence of 2 to 8%, and exclusion of 150 HPV vaccinated women from the analysis, we would have approximately 80% power to detect an absolute increase in overall HPV prevalence of at least 2 to 4% (see table below). Exploratory analyses of changes in HPV prevalence by gender and age and by vaccination status will be descriptive.

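### The age model and the comparison at age 14 make no allowance for HPV vaccination, so any vaccine protection in females aged 12 to 24 would make acquisition look later than it is

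*Protocol*

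**What the plan says.** **Primary analysis (Protocol 12.2.1).** Prevalence is the "number of patients with HPV detected in tonsils divided by the total number of patients with available samples", overall and by age and gender group. The relation with age is then explored by "logistic regression with the age as a continuous covariate and gender and centre as categorical covariate". Only the polynomial degree and a possible transformation of age are left open.

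**Age comparison (12.3).** Sampling is stratified so that patients aged 14 and under, labelled non-exposed, can be compared with older patients, labelled exposed. The stated purpose is "to allow the determination of the age of acquisition of infection and the optimal age of start of vaccination". No analysis set or adjustment is given.

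**Vaccinated patients.** The eligibility criteria (4.1, 4.2) do not exclude them. Section 7 collects vaccination history, including dates, doses and vaccine type. The power calculation for the historical comparison (12.4) assumes "exclusion of 150 HPV vaccinated women from the analysis". Section 12.2.2 plans an exploratory comparison of vaccinated and unvaccinated females aged 12 to 24. It also plans a risk-factor model for HPV DNA in the tonsil, in which vaccination status is one example of a candidate variable.

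**The concern.** Vaccination is tied to sex, because section 1.3 says that member states with programmes vaccinate girls only. It is tied to age through the 12-to-24 target class, which straddles the cut at 14. If it also lowers the HPV detected, it confounds the age curve in the very years where acquisition is looked for. Prevalence in young females would be held down by vaccination, and the plan would read that as a later or weaker rise with age.

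What is at stake is the inference about age of acquisition and of vaccination start, which would rest partly on a curve that vaccination had already altered. The prevalence objective is not at stake: vaccinated patients belong in an estimate of current prevalence.

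**Working it through.** **Plan's own figures.** The protocol gives no power or precision for the age comparison. The nearest figure is Table 7: 80% power with 1100 per cohort. The two-proportion normal approximation with continuity correction gives 78.3%, 81.4% and 79.1% for its three rows, so the table reproduces to within 2 points. Its 1100 equals 1250 - 150, and Figure 1's caption also refers to 1250, whereas the text says "We plan to enrol 925 patients". The 150 therefore appears to belong to a cohort of 1250. Scaled to 925 it is 150 x 925/1250 = 111. Both values are carried below.

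**Inputs from Table 6.**
- Aged 14 and under: 3 x 150 = 450. Over 14: 925 - 450 = 475.
- Half female, as in the pilot data under Table 5. Ages 10-14 are taken as evenly spread (assumed).
- Females 12-14: 150 x 3/5 x 1/2 = 45. Females 15-24: 300 x 1/2 = 150. Total 195.
- Vaccinated share, if all vaccinated women are in this band: 111/195 = 57% to 150/195 = 77%.
- Spread evenly over the band: 26 to 35 vaccinated at 12-14 (nv x 45/195) and 85 to 115 at 15-24 (nv x 150/195).

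**Assumed.** Section 1.5 says there are no data on vaccine effect in the mouth. A reduction r of 50-90% in detected HPV is used as illustration, not as an estimate.

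**Comparison at age 14.**
- Observed over 14 = p2 x (1 - r x v2/475), with v2 = 85.4 or 115.4.
- Observed at 14 and under = p1 x (1 - r x v1/450), with v1 = 25.6 or 34.6.
- Mildest case, p1 = 2%, p2 = 6.5%, 111 vaccinated, r = 0.5: 6.5 x (1 - 0.5 x 85.4/475) = 5.92%; 2 x (1 - 0.5 x 25.6/450) = 1.94%; difference 3.97 points.
- Strongest case, 150 vaccinated, r = 0.9: 6.5 x (1 - 0.9 x 115.4/475) = 5.08%; 2 x (1 - 0.9 x 34.6/450) = 1.86%; difference 3.22 points.

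Power below is two-sided at 0.05, pooled, without continuity correction.

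| True prevalence (14 and under v over 14) | True difference | Observed difference | Power with no vaccine effect | Power, vaccinated kept and unadjusted |
|---|---|---|---|---|
| 2% v 4.1% | 2.1 | 1.3-1.8 | 46% | 25-37% |
| 2% v 6.5% | 4.5 | 3.2-4.0 | 92.5% | 76-88% |
| 2% v 8% | 6.0 | 4.4-5.3 | 98.8% | 92-97% |
| 5% v 10% | 5.0 | 3.2-4.2 | 82% | 51-72% |

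Across these scenarios the difference shrinks by about 11-37%. With vaccinated women left out, power for 2% v 6.5% is 88-89%.

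**Females aged 15-24 alone.** Observed = p2 x (1 - r x v2/150). A true 8% appears as 2.5-5.7%. A true 4.1% appears as 1.3-2.9%, against 2% in childhood.

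**Logistic age model.** A cubic in age with a gender main effect was fitted to expected values under a true step from 2% to 8% at age 15 (centre left out). The measure is the first whole year of age at which fitted prevalence reaches 5%.

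| Model | Males | Females |
|---|---|---|
| No vaccine effect | 15 | 15 |
| Vaccine effect 50-90%, no vaccination term | 16-17 | 19-27 |
| Same, with vaccination term (curve for unvaccinated) | 15 | 16 |

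The male curve moves slightly because both sexes share one age shape. With a straight line in age, the vaccination term corrects the female curve only in part.

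**The case against.** Four objections deserve weight.

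1. **This is detail for the SAP.** Section 12.2 defers detail to a SAP and presents the age model as exploration. The acquisition purpose stands in 12.3, as the reason for the sampling, not in 12.2.1. That is fair, and that vaccinated women stay in the comparison at 14 is inferred from the absence of any exclusion. But 12.2.1 does name the covariates, vaccination is not among them, and 12.4 shows that the issue was recognised for another analysis.

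2. **Section 12.2.2 already covers vaccination.** The tonsil risk-factor model may include it on grounds of possible causal relationship, and females aged 12 to 24 are compared by vaccination status. This is partial mitigation. The term is optional, and neither analysis is tied to age of acquisition.

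3. **Males are not directly affected**, sex-specific prevalence is planned, and the rationale in 1.5 is about boys. This stands and limits the harm. Only the shared age shape carries some distortion into the male curve.

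4. **Excluding vaccinated women leaves very few young females.** Of 195, 195 - 150 = 45 to 195 - 111 = 84 remain. At 8% prevalence, 45 females give 45 x 0.08 = 3.6 expected positives, and non-vaccinees are self-selected. This stands, and it is why adjustment is preferred to exclusion as the main analysis.

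A reader might infer that acquisition would look absent. The figures do not show that for the comparison at 14, where the difference shrinks but persists. A vanishing rise appears only in females aged 15-24, when the true rise is small or protection is high.

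**Conclusion.** The point holds as a modest, inexpensive improvement. As written, the age model and the comparison at 14 let any vaccine effect in females aged 12 to 24 pass as an age effect, so acquisition appears later, mainly in females. Under assumed effects of 50-90% and 111-150 vaccinated women, a true 4.5-point difference across age 14 becomes about 3.2-4.0 points, and the female age curve can move by several years.

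The direction requires that the vaccine reduces the HPV types detected; the size rests on the assumed effect, an even sex split and all vaccinated women being in the band. A reader might take 150 as the firm count for this cohort, or conclude that vaccinated patients bias the prevalence estimates. The documents support neither: the 150 appears to come from a cohort of 1250, and including these patients is right for the primary objective.

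**What to change.** - Keep all patients with available samples for overall, age-specific and gender-specific prevalence.
- In 12.2.1, state that when the logistic model is used for age of acquisition, HPV vaccination status is added as a covariate, and that the curve is read for unvaccinated patients. Choose the degree of age with that term in the model.
- In 12.3, state that the comparison at 14 is adjusted for, or stratified by, vaccination status.
- Add a sensitivity analysis of both in unvaccinated patients only.

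**Cost.** One model term, one repeat run and no new data, since vaccination status is already collected. The price is a wider interval for females aged 12 to 24, because only about 45-84 of them would be unvaccinated. The sensitivity analysis will be least precise there and should be reported as such.

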2.1. OBJECTIVES

2.1.1. PRIMARY OBJECTIVE:

• To estimate the overall, age and gender specific prevalence of HPV in the oropharynx in patients undergoing tonsillectomy for non-malignant conditions

2.1.2. SECONDARY OBJECTIVES:

- To compare the HPV oropharynx prevalence between different sites—in order to identify the different reservoirs of HPV infection
- To describe the distribution of HPV seropositivity in the study population by age and gender
- To describe HPV-type distribution overall by age, gender, and sampling site
- To describe distribution by age and gender of patients who are both HPV PCR positive and anti-HPV L1 sero-positive – predicting persistent HPV infection
- To provide preliminary estimates of the clearance and persistence of HPV infection and antibodies in the oropharynx, as detected in follow-up oral fluid, finger tips/nail brushings and urine samples
- To assess the presence of anti-L1 HPV antibodies in saliva as a marker of vaccination or previous infection in the oral cavity
- To assess the presence of HPV in the urine
- To assess the presence of HPV in finger tips/nail brushings
- To provide preliminary evaluation of the performance of potential non-invasive tests for the detection of HPV infection in the mouth against HPV detection rates in tonsillectomy and oropharyngeal scrapes
- To identify the change in overall prevalence and distribution of HPV in tonsils over time, and to describe preliminary data on age and gender specific changes over time
- To provide preliminary data on the potential effect of HPV vaccination in the prevention of oral infection

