2.2. OUTCOME MEASURES

2.2.1. PRIMARY OUTCOME

Occurrence of HPV in tonsil samples

[figure not shown]

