7. STUDY PROCEDURES AND SAMPLE COLLECTION

All samples should be collected in accordance to the study procedure manual developed by GSK with details of sample collection kits, volume of samples to be collected and storage temperature requirements.

For a patient to be eligible for inclusion in the data analysis, the following samples are a minimum requirement:

- Oral samples
- Blood
- Oropharyngeal brushings
- Tonsils

 After written consent is obtained, the patients (above 16 years old only) will complete a short study questionnaire including age, gender, history of tobacco/alcohol use, sexual history including age of start of sexual intercourse, lifetime numbers of sexual partners, engagement in oral sex and lifetime number of oral sex partners etc.

- 2. An HPV vaccination history will also be taken. Consent/assent will also be taken from the patient, parent(s) or their guardian(s), if applicable, to obtain the patient's HPV vaccination status from vaccine and medical health records from their GP and/or other relevant health and educational authorities. The data requested will include confirmation of HPV vaccination status, including dates, number of doses and the type of vaccine given.
- 3. Oral fluid samples will be collected for HPV PCR and HPV antibody tests, using an oral rinse and an exudate collection device respectively.
- 4. A 20 30 ml urine sample will be collected for HPV PCR test.
- 5. Blood serum will be taken for HPV and biomarker serology tests. This can be taken after the patient has been anaesthetised if necessary. 20 mls of blood will be taken from patients aged 16 years and above, 10 mls from patients below 16 years old.
- 6. Once the patient is anaesthetised, two brush cytology scrapings using cytobrushes (provided) will be taken: one from the posterior pharynx including above and below the soft palate so that the adenoidal area is included, and a second separate brush scrape will be taken from the back of the tongue (base of tongue).
- 7. Tonsillectomy will then be performed and the tonsillar tissue will be placed in 10% buffered formalin and sent to the pathology department for paraffin embedding according to a specific protocol.
- 8. Stratified sampling will be employed to ensure that sufficient numbers of patients are recruited from all age groups, especially the age groups between 10 and 20 years old.

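### Section 12.2.2 takes the oral sample as reference for sensitivity and specificity, whereas the objective sets non-invasive tests against tonsil tissue and oropharyngeal scrapes

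*Protocol*

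**What the plan says.** The secondary objective in Protocol section 2.1.2, repeated in the Study Summary, is a preliminary evaluation of "potential non-invasive tests for the detection of HPV infection in the mouth against HPV detection rates in tonsillectomy and oropharyngeal scrapes".

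Section 12.2.2 is where this objective is analysed:

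- **HPV detection.** Kappa is computed between tonsils on one side and scrapes, oral fluid and urine on the other. The next sentence says that specificity, sensitivity, PPV and NPV of "HPV detection in the different sample types will be derived using the oral sample results as the reference".
- **Anti-L1 antibody in oral fluid.** For kappa, antibody presence and "occurrence of HPV in tonsils and/or in oropharyngeal scrape samples will be analysed by computing kappa". The next sentence says that the accuracy measures "of anti-HPV L1 antibody assay will be derived using the oral sample results as the reference".

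On terms, section 7 lists oral samples, oropharyngeal brushings and tonsils as three separate items in the minimum sample set. It also states: "Oral fluid samples will be collected for HPV PCR and HPV antibody tests, using an oral rinse and an exudate collection device respectively". Table 3 in section 7.4 likewise lists oral rinse apart from tonsils and oropharyngeal brushings. The primary outcome in section 2.2.1 is "Occurrence of HPV in tonsil samples".

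**The concern.** The objective and the analysis put different specimens in the reference role. Under the objective, tonsil tissue and scrapes are the standard, and oral fluid, urine and nail brushings are the candidates. Under section 12.2.2, one candidate becomes the standard, and tonsil, the primary-outcome specimen, becomes one of the tests judged against it. The comparator also changes between adjacent sentences: kappa is anchored on tonsil (or tonsil and/or scrapes), while sensitivity and specificity are anchored on the oral sample.

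What is at stake is how the results would be read. Section 1.4 says that the data matter for evaluating screening programmes, and section 12.2.2 plans to look for screening markers. A figure labelled sensitivity that is really a predictive value could mislead anyone asking how much tonsillar infection a non-invasive sample would miss. The protocol fixes the reference explicitly, so this is not a detail left for the SAP.

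**Working it through.** The protocol states no diagnostic-accuracy figure, so there is none to reproduce. The check has two parts.

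**1. The roles side by side**

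| Place | Tests evaluated | Comparator |
|---|---|---|
| Objective, 2.1.2 | Non-invasive samples | Tonsil tissue and oropharyngeal scrapes |
| 12.2.2, kappa for HPV detection | Scrapes, oral fluid, urine | Tonsil |
| 12.2.2, accuracy of HPV detection | The different sample types | Oral sample |
| 12.2.2, kappa for anti-L1 | Antibody in oral fluid | Tonsil and/or scrapes |
| 12.2.2, accuracy of anti-L1 | Antibody assay | Oral sample |

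Only the two accuracy rows depart from the objective.

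**2. What reversing the reference does**

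Let a = both positive, b = oral only, c = tonsil only, d = both negative.

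- Tonsil as reference: sensitivity a/(a+c), specificity d/(b+d), PPV a/(a+b), NPV d/(c+d).
- Oral sample as reference: sensitivity a/(a+b), specificity d/(c+d), PPV a/(a+c), NPV d/(b+d).

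Sensitivity and PPV trade places, as do specificity and NPV. This is algebra and needs no assumption. The figure labelled sensitivity becomes (true sensitivity against tonsil) × (tonsil prevalence ÷ oral prevalence).

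Inputs for an illustration:

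- N = 925 (section 12.3).
- Oral prevalence 6.5% (section 12.3, literature figure).
- Tonsil prevalence 2–8% (section 12.4, baseline range for the historical comparison), with 5% as a middle value.
- The share of tonsil positives that oral fluid detects is not in the protocol. It is assumed to be 30–90%.

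Worked case, tonsil 5% and detection 60%:

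- Tonsil positives 925 × 0.05 = 46.25; oral positives 925 × 0.065 = 60.125.
- a = 0.60 × 46.25 = 27.75; b = 60.125 − 27.75 = 32.375; c = 46.25 − 27.75 = 18.5; d = 925 − 27.75 − 32.375 − 18.5 = 846.375.

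| Measure | Tonsil as reference | Oral sample as reference |
|---|---|---|
| Sensitivity | 27.75/46.25 = 60.0% | 27.75/60.125 = 46.2% |
| Specificity | 846.375/878.75 = 96.3% | 846.375/864.875 = 97.9% |
| PPV | 46.2% | 60.0% |
| NPV | 97.9% | 96.3% |

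Kappa is 0.493 with either reference.

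Range over the assumed detection:

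- Tonsil 5%, oral 6.5%: 30–90% is reported as 0.30 × 5/6.5 = 23.1% to 0.90 × 5/6.5 = 69.2%.
- Tonsil 2%, oral 6.5%: 30–90% is reported as 0.30 × 2/6.5 = 9.2% to 0.90 × 2/6.5 = 27.7%.
- Tonsil 8%, oral 6.5%: the shift goes the other way. A sensitivity of 60% is reported as 0.60 × 8/6.5 = 73.8%.

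For urine, nail brushings and, on the plain reading, the antibody assay, the stated analysis cross-tabulates against the oral sample. Their accuracy against tonsil or scrapes is in none of those tables, so relabelling cannot recover it.

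**The case against.** Several points on the other side are sound and limit the finding.

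- A reader might infer that the objective cannot be answered at all. The protocol does not support that. The tonsil-anchored kappa covers scrapes, oral fluid and urine, does not depend on the reference, and serves an objective described as preliminary. Kappa is not a full substitute, though. It is symmetric, so it cannot separate missed infection from over-calling, and the kappa sentence does not list nail brushings.
- A reader might infer that oral fluid gets no result. That is also too strong. All four measures for oral against tonsil, and for oral against scrapes, are produced under exchanged names.
- The oral sample is never formally defined. Table 1 in section 1.4 uses the term broadly, covering scrapings, brushes and swabs. In the antibody paragraph the HPV results named just before are those in tonsils and/or scrapes, so the reference there may point back to them. That sentence is therefore ambiguous rather than clearly reversed. In the HPV-detection sentence the broad reading is hard to sustain, because section 7 separates oral samples from brushings and tonsils.
- The protocol does not rank oral fluid above urine or nail brushings, so it should not be called the leading candidate.
- Tonsil alone is not the only defensible standard. The objective names tonsil and scrapes, and some oral-only positives could be scrape-positive. The illustrative specificities apply to a tonsil reference only.
- The paired data will exist whichever reference is written down, so the intended measures can still be computed later. That lowers the severity but does not make the stated rule right.

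**Conclusion.** The HPV-detection accuracy sentence in section 12.2.2 is wrong as written, because it contradicts the objective it serves. The exchange of sensitivity with PPV and of specificity with NPV for the oral–tonsil and oral–scrape pairs is certain. So is the absence of accuracy figures for urine and nail brushings against tonsil or scrapes. The antibody sentence is ambiguous but needs the same correction on either reading.

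The size is illustrative only. It rests on the prevalences taken from sections 12.3 and 12.4 and on assumed agreement between samples. A reader might infer that the plan always understates oral-fluid sensitivity; it does so only when oral prevalence exceeds tonsil prevalence.

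Severity is moderate. The objective is secondary and preliminary, and the primary prevalence analysis and the kappa coefficients are untouched. It should be corrected before analysis, so that the reference is not chosen once results are known.

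**What to change.** In section 12.2.2, replace the closing clause of both accuracy sentences with wording such as: *with HPV detection in tonsil tissue, and HPV detection in tonsil tissue and/or oropharyngeal scrapes, as the two references*. In the same place:

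- Name the index tests: HPV in oral fluid, urine and nail brushings, and anti-L1 antibody in oral fluid.
- Define the oral sample once. The vaccine case-control analysis in section 12.2.2 also uses the term, to define cases and controls.
- Report exact 95% confidence intervals for each measure. At tonsil prevalence 2–8%, 925 patients give only about 925 × 0.02 = 18.5 to 925 × 0.08 = 74 tonsil positives, so sensitivity will rest on small denominators.

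No new samples, tests or patients are needed. Two references in place of one, with intervals, add a few tabulations on data already collected.
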